7.12.3 Best-Corrected Visual Acuity (BCVA)

Where there are more than one BCVA measurement at the same visit, the median value will be used for the purpose of the analysis.

Part I

BCVA actual values and change from baseline at 1, 3, 6, 9, 12, 18, and 24 months will be summarized by treatment groups, visits, and eyes based on observed case. The 95% CI for mean values and mean change from baseline will be provided.

Furthermore, the proportion of eyes with BCVA gain from baseline ≥ 5 , 10, 15 letters will be summarized by treatment groups, visits and eyes. The proportion of eyes with BCVA change from baseline > -5 letters measuring the maintenance of BCVA will also be summarized by treatment groups, visits, and eyes. The 95% CI will be provided by using the Clopper-Pearson method.

Part II

Change from baseline in BCVA at 1, 2, 3, 6, 9, and 12 months will be summarized by descriptive statistics. The 80% CI for mean values and mean change from baseline will be provided. Observed data collected within 6 months of the last visit window will be used regardless of intercurrent events, i.e. discontinuation of study early or lost to follow up.

For handling the missing data imputation for analyzing the change from baseline, the primary analysis is:

MMRM model will be applied to analyse the mean change from baseline, using fixed effects of treatment groups (high dose, low dose, and untreated), study visit, study visit-by-treatment interaction, baseline BCVA value and baseline-by-visit interaction. An unstructured covariance matrix will be used to model the within-patient variance-covariance errors. If the unstructured covariance structure matrix results are in a lack of convergence, the heterogeneous Toeplitz covariance structure followed by the heterogeneous first-order autoregressive covariance structure will be used. The Kenward-Roger approximation will be used to be missing at random.

The proportion of eyes with BCVA gain from baseline ≥ 5 , 10, 15 letters, as well as the BCVA change from baseline >-5 (maintenance) will be summarized based on observed case

within each group and the 80% CI for proportion will be calculated by the Clopper-Pearson method. For BCVA gain from baseline ≥ 10 and ≥ 15 letters, where subjects are expected to show more pronounced improvement in treated eyes than non-treated eyes, the difference in proportion between the treatment group and control group will be presented with its corresponding 80% CI calculated using the method of Miettinen and Nurminen (Ref. Miettinen and Nurminen, 1985), and the p-value will be reported by the Fisher's Exact-Boschloo test with a Berger-Boos correction of beta=0.001(Berger 1994). In the event of missing BCVA data, the primary analysis to analyse the proportion of study eyes with BCVA gain or maitenenace from baseline is LOCF approach.

To account for BCVA data from one site impacted by a protocol deviation involving assessments conducted by an unmasked rather than masked assessor from month 3 to month 12, a sensitivity analysis will be conducted evaluating safety signals for BCVA loss from baseline. A summary table of BCVA loss from baseline $\geq 5, \geq 10, \geq 15$ letters will be summarized at each visit, by excluding BCVA data impacted by unmasking.

7.12.4 Low Luminance Visual Acuity (LLVA)

When LLVA are measured in triplicates, the median value will be used for analysis.

Part I

LLVA actual values and change from baseline will be summarized by treatment groups, visit, and eyes. The 95% CI for mean values and mean change from baseline will be provided. The proportion of eyes with LLVA gain from baseline \geq 5, 10, 15 letters will be summarized, as well as the proportion of eyes with LLVA change from baseline > -5 letters will be summarized. The 95% CI will be provided by using the Clopper-Pearson method.

Low luminance deficit (LLD) is the difference between BCVA and LLVA. LLD observed values and change from baseline will be summarized by treatment groups, visits, and eyes.

Part II

The analysis conducted for BCVA will be applied to LLVA. The primary analysis for handling missing data for change from baseline is using MMRM model.

The proportion of eyes with LLVA gain from baseline ≥ 5 , 10, 15 letters, as well as the LLVA change from baseline \geq -5 letters (maintenance) will be summarized within each group and the 80% CI for proportion will be provided. For LLVA gain from baseline \geq 10 and \geq 15 letters, where subjects are expected to show a more pronounced improvement in treated eyes than non-treated eyes, the difference in proportions between treatment group and control group will be presented with its corresponding 80% CI calculated by Miettinen and Nurminen, and the p-value will be reported by the Fisher's Exact-Boschloo test with a Berger-Boos correction of beta=0.001.In the event of missing LLVA, the primary analysis of the proportion of study eyes with LLVA gain or maintenance from baseline is the LOCF approach.

LLVA data from one site were impacted by a protocol deviation involving assessments conducted by an unmasked rather than masked assessor from month 3 to month 12. LLVA improvement from baseline is regarded as an efficacy endpoint. To further detect the impact of unmasking on this efficacy signal, a sensitivity analyses will be conducted to summarize the proportion of eyes with LLVA change from baseline ≥ 5 , ≥ 10 , and ≥ 15 letters, as well as change from baseline ≥ -5 (maintenance) at Month 12, by excluding LLVA data impacted by unmasking at Month 12.

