5.2.2.3 Secondary Endpoints

- Change from baseline in microperimetry
 - Proportion of study eyes with ≥7 dB improvement from baseline at ≥5 of the 16 central loci in microperimetry at 1, 2, 3, 6 and 9 months, respectively
 - Proportion of study eyes with ≥7 dB improvement from baseline at ≥5 of the 68 loci in microperimetry at 1, 2, 3, 6, 9 and 12 months, respectively
 - Change from baseline in Mean Sensitivity of the 16 central loci at 1, 2, 3, 6, 9 and 12 months, respectively
 - Change from baseline in Mean Sensitivity of the 68 loci at 1, 2, 3, 6, 9, and 12 months, respectively

- Change from baseline in BCVA and LLVA
 - Change from baseline in BCVA and LLVA at 1, 2, 3, 6, 9, and 12 months, respectively
 - Proportion of eyes with a \ge 15 letter increase from baseline at 1, 2, 3, 6, 9, and 12 months, respectively
 - Proportion of eyes with a \ge 10 letter increase from baseline at 1, 2, 3, 6, 9, and 12 months, respectively
 - Proportion of eyes with a \geq 5 letter increase from baseline at 1, 2, 3, 6, 9, and 12 months, respectively
 - o Proportion of eyes with a ≥15 letters loss from baseline for BCVA and LLVA at 1, 2, 3, 6, 9, and 12 months, respectively
 - o Proportion of eyes with a ≥10 letters loss from baseline for BCVA and LLVA at 1, 2, 3, 6, 9, and 12 months, respectively
 - o Proportion of eyes with a ≥5 letters loss from baseline for BCVA and LLVA at 1, 2, 3, 6, 9, and 12 months, respectively
 - Proportion of eyes with change from baseline > -5 letters for BCVA and LLVA at 1, 2, 3, 6, 9, and 12 months, respectively
- Change from baseline in visual field assessed by Octopus 900 at 3, 6 and 12 months, respectively

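### SAP 7.12.4 Part II counts an LLVA change of exactly -5 letters as maintained, but the stated endpoint (> -5 letters) does not

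*SAP*

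**What the plan says.** The Part II endpoint list in SAP 5.2.2.3 gives one strict category for both acuity measures, "Proportion of eyes with change from baseline > -5 letters for BCVA and LLVA at 1, 2, 3, 6, 9, and 12 months", and beside it the loss category "Proportion of eyes with a ≥5 letters loss from baseline for BCVA and LLVA at 1, 2, 3, 6, 9, and 12 months". Read together, the two are exact complements.

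The analysis sections mostly keep the strict cutoff. For BCVA in Part II, SAP 7.12.3 plans that the "BCVA change from baseline >-5 (maintenance) will be summarized based on observed case". For LLVA in Part I, SAP 7.12.4 states that "the proportion of eyes with LLVA change from baseline > -5 letters will be summarized".

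The Part II text of 7.12.4 departs from this twice. In the main summary, a greater-than-or-equal sign and a minus sign stand directly before the words "5 letters (maintenance) will be summarized within each group and the 80% CI for proportion will be provided". The sensitivity summary that leaves out data from the unmasked assessors repeats the inclusive cutoff: "as well as change from baseline ≥ -5 (maintenance) at Month 12". The same Part II text opens by saying that the BCVA analysis carries over to LLVA, and that analysis uses > -5.

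SAP 7.13.3 separately tabulates LLVA decreases of at least 5, 10 and 15 letters as a safety summary.

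**The concern.** A programmer cannot satisfy 5.2.2.3 and 7.12.4 Part II together. If 7.12.4 is followed, the table reports a proportion that is not the listed secondary endpoint. If 5.2.2.3 is followed, the output departs from the analysis section. Either way the operator is chosen during programming, when it should have been fixed in advance.

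The boundary value can occur. Protocol 10.7 reports LLVA as the number of letters read correctly, so changes are whole letters, and the SAP's median of three readings is again a whole number. An eye at exactly -5 would then be described as maintained in one place and as a loss in another. The error runs one way: the inclusive rule can only give a maintenance rate equal to or higher than the strict one.

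**Working it through.** The plan gives no figure to reproduce here. The check has three parts: the category definitions, the effect of one eye, and a rough frequency.

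**1. Which values are affected.** Three rules were applied to whole-letter changes: loss of at least 5 (5.2.2.3 and 7.13.3), change > -5 (5.2.2.3, 7.12.3, LLVA Part I) and change ≥ -5 (LLVA Part II).

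| Change in letters | Loss ≥ 5 | > -5 | ≥ -5 |
|---|---|---|---|
| -7 | yes | no | no |
| -6 | yes | no | no |
| -5 | yes | no | **yes** |
| -4 | no | yes | yes |
| -3 | no | yes | yes |

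Only -5 is affected. With > -5, every whole-letter change is in exactly one of the two categories. With ≥ -5, a change of -5 is in both.

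**2. Effect of one eye.** SAP 6.6 bases its power calculation on 10 subjects in a dose arm and 9 in the control arm. One reclassified eye moves the proportion by 1/10 = 10.0 points or 1/9 = 11.1 points. With 80% Clopper-Pearson intervals, the SAP's method, and illustrative counts:

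- n = 10: 8/10 = 80% (55.0 to 94.5) becomes 9/10 = 90% (66.3 to 99.0).
- n = 9: 7/9 = 77.8% (51.0 to 93.9) becomes 8/9 = 88.9% (63.2 to 98.8).

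**3. How often -5 might occur.** The documents give no standard deviation for LLVA change. Assume that the change is roughly normal with mean 0. Then P(-5.5 < change < -4.5) is 0.048 for SD 5, 0.044 for SD 7, 0.041 for SD 8 and 0.035 for SD 10.

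- Expected eyes at -5 in an arm of 10 at one visit: 10 × 0.035 to 10 × 0.048 = 0.35 to 0.48.
- Chance of at least one in an arm of 10, with independent eyes: 1 - 0.965^10 = 0.30 to 1 - 0.952^10 = 0.39.
- Chance of at least one among 10 + 10 + 9 = 29 study eyes: 1 - 0.965^29 = 0.64 to 1 - 0.952^29 = 0.76.

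Under these assumptions, at least one eye in the trial would more likely than not be affected at Month 12.

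**4. Is it a deliberate choice, or a flaw in the PDF text?** Neither is likely. No section gives a reason for a different LLVA cutoff in Part II, and the SAP's summary of changes does not mention one. The inclusive sign appears twice and is rendered in two different ways, while the Part I paragraph of the same section keeps the strict sign.

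**The case against.** The strongest reply is that little depends on this. LLVA maintenance receives only a within-group proportion and an 80% interval. Between-group differences and Boschloo p-values are specified in 7.12.4 only for gains of at least 10 and 15 letters. The rule is the same in all arms, so it does not by itself favour treated eyes. The main and sensitivity summaries share it, so that robustness check is internally consistent. The intended reading can also be partly recovered from 5.2.2.3 and from the carry-over from BCVA. All of this stands. It limits the size of the problem but does not remove the contradiction.

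A reader might infer more than the documents support in two respects.

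- **That the loss and maintenance percentages would otherwise sum to 100%, and now exceed it.** LLVA loss is analysed in 7.13.3 on the Safety Analysis Set, on observed cases. Maintenance is analysed on the ITT set, with LOCF as the primary handling of missing values. The Part II safety set can also include subjects from the earlier two-arm randomisation (three were randomised), who are outside the ITT set. The two figures need not sum to 100% even after correction. What survives is that one eye can appear in both tables.
- **That LLVA cannot be compared with BCVA or with Part I.** Only one value is affected, so these comparisons are slightly misaligned but still possible. No formal comparison of either kind is planned.

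On wording, the endpoint lists and the Part I LLVA text do not call the > -5 category maintenance. That label comes from 7.12.3 and 7.12.4 Part II, but the category is plainly the same.

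**Conclusion.** The inconsistency is real and can be seen in the text alone. As written, 7.12.4 Part II does not analyse the LLVA endpoint listed in 5.2.2.3, and an eye at exactly -5 letters is counted as maintained although 5.2.2.3 and 7.13.3 class it as a loss of at least 5 letters. The definitional result needs no assumption beyond whole-letter scoring. The step of 10 or 11.1 points per eye rests on the planned arm sizes. The frequency of 3.5 to 4.8% of eyes rests on an assumed mean of 0 and SD of 5 to 10 letters, which the documents neither give nor contradict.

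The consequence is modest: a descriptive secondary proportion that can be slightly too high. The primary endpoint, the Hochberg procedure, alpha and power do not depend on it. It should still be corrected, because this is a wrong analysis rule for a listed endpoint and the correction is trivial.

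**What to change.** In SAP 7.12.4 Part II, replace the inclusive cutoff with > -5 letters in both places: the main maintenance summary and the Month 12 sensitivity summary. This restores agreement with 5.2.2.3, 7.12.3, LLVA Part I and the loss category in 7.13.3. Moving everything to ≥ -5 instead would need more edits and would still overlap with the loss category.

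The cost is two operators. No new data or change of method is needed. The reported LLVA maintenance rate may be slightly lower.

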7.12.5 Spectral Domain Optical Coherence Tomography (SD-OCT)

Part I and Part II

For foveal subfield thickness, central horizontal ellipsoid width (μ m), central ellipsoid area (mm²), choroidal thickness at foveal center, and total macular volume change from baseline will be summarized by treatment groups, visits and eyes based on observed case.

For presence of vitreomacular traction (VMT), epiretinal membrane (ERM), macular hole in vitreo-macular interface disease, cystoid macular edema, subretinal fluid, and targeted ocular findings (TOF) will be summarized by treatment groups, visits, and eyes.

The shift table for VMT, ERM and macular hole will be summarized from "absent", or "present" at baseline to "absent" or "present" at any post-baseline visit.

The shift table for cystoid macular edema and subretinal fluid will be summarized from "none", "Yes, foveal" or "Yes, non-foveal" at baseline to "none", "Yes, foveal", or "Yes, non-foveal" at any post baseline visit.

7.12.6 Fundus Autofluorescence

Part I and Part II

For total area of preserved autofluorescence and distance from foveal center (FC) to nearest border of preserved autofluorescence, their observed value and change from baseline will be summarized by treatment groups, visits and eyes based on observed case.

The number and percentage of subjects with subfoveal or non-subfoveal location of lesion in relation to foveal center, and presence of targeted ocular findings (TOF) will be summarized by treatment groups, visits, and eyes.

The shift from baseline in the location of lesion in relation to autofluorescence will be summarized from "subfoveal", or "non-subfoveal" at baseline to "subfoveal", or "non-subfoveal" at any post baseline visit.

7.12.7 Visual Fields

Part I and Part II

When there is more than one visual field measurement at the same visit, the average will be used for the purpose of the analysis.

The Reliability Factor (RF) is equal to (number of false positive responses + number of false negative responses) divided by (number of false positive presentations + number of false negative presentations) times 100. If there are 0 responses, then the RF value is equal to 0. RFpositive is defined as (number of false positive responses) divided by (number of false positive presentations) times 100.

If $RF \le 20\%$ the measurement is considered reliable. If $20\% < RF \le 25\%$ and RF positive $\le 10\%$ the measurement is also considered reliable. Otherwise if $20\% < RF \le 25\%$ and RF positive > 10%, or RF > 25%, the measurement is not reliable.

For reliable measurement from the volume of full field hill of vision and volume of 30-degree hill of vision, their observed values and change from baseline will be summarized by treatment groups, visits and eyes on observed case. In addition, summary tables from full records of full field hill of vision and volume of 30-degree hill of vision will be also

provided. A listing including all records, as well as an indication of reliable records will be provided.

7.12.10 Contrast Sensitivity

Part I and Part II

Contrast Sensitivity Score (CSS) and change from baseline will be summarized by treatment groups, visits and eyes by observed case.

7.13 Safety Analysis

Safety analysis will be performed using the Safety Analysis Set. All safety analyses will be summarized based on observed case.

- Time to onset of first occurrence of Visual Acuity Reduced-related TEAEs by SOC and PT, and by time to onset (≤30 days; >30 days)
- Time to onset of first occurrence of Visual Acuity Reduced-related TEAEs by SOC and PT, and by time to onset (≤90 days; >90 days)

For example, if a subject has multiple TEAE events on the same preferred term level, the first occurrence within each latency period is counted. i.e. if a subject has multiples TEAEs on the same preferred term level where some start within ≤ 30 days and others start > 30 days post treatment, the first TEAE record within ≤ 30 days is counted. Similarly the first TEAE record > 30 days is counted.

AEs will be coded using MedDRA version 23.1.

In addition, TEAE will be summarized in the following tables:

- Overall summary of TEAE
- TEAEs by SOC and PT sorted by decreasing frequency
- Dose Limiting Toxicity (DLT) AEs, by SOC and PT
- TEAEs with an incidence of 10% or more in any treatment group, by SOC and PT
- Study drug-related only TEAEs by SOC and PT
- Study procedure-related only TEAEs by SOC and PT
- Study drug and study procedure related TEAEs, by SOC and PT

- Related TEAEs but with unknown attribution to study drug or study procedure, by SOC and PT
- SAEs by SOC and PT sorted by decreasing frequency
- Study drug-related SAEs, by SOC and PT (only study drug-related)
- Study procedure-related SAEs, by SOC and PT (only study procedure-related)
- Study drug and study procedure related SAEs, by SOC and PT
- Related SAEs but with unknown attribution to study drug or study procedure, by SOC and PT
- TEAEs by maximum severity, by SOC and PT

The following AE listings will be provided:

- Ocular adverse event treatment emergent
- Ocular adverse event non-treatment emergent
- Non-ocular adverse event treatment emergent
- Non-ocular adverse event non-treatment emergent
- Serious adverse events (SAEs)
- SAEs leading to discontinuation from the study
- A listing of death

7.13.2 Best-Corrected Visual Acuity (BCVA)

Part I and Part II

The proportion of eyes with a \geq 5 letters, a \geq 10 letters and a \geq 15 letters decrease from baseline will be summarized by treatment groups, visits, and eyes.

When there are more than one BCVA measurement at the same visit, the median value will be used for the purpose of the analysis.

7.13.3 Low Luminance Visual Acuity (LLVA)

Part I and Part II

The proportion of eyes with a \geq 5 letters, a \geq 10 letters and a \geq 15 letters decrease from baseline will be summarized by treatment groups, visits, and eyes.

When there are more than one LLVA measurement at the same visit, the median value will be used for the purpose of the analysis.

7.13.4 Dilated Ophthalmoscopy

Part I and Part II

The number and percentage of subjects within each category of each Dilated Ophthalmoscopy outcomes will be summarized by treatment groups, visits and eyes. Shift from baseline will also be evaluated. The shift for "Vitreous", "Macula", "Peripheral retina", "Choroid" and "Optic nerve" will be summarized from "Normal/Clinically insignificant abnormality", or "Clinically significant abnormality" at baseline to "Normal/Clinically insignificant abnormality", or "Clinically significant abnormality" at any visit post-baseline.

The shift for "Retinal tear(s)" and "Retinal detachment" will be summarized from "Absent", or "Present" at baseline to "Absent", or "Present" at any visit post-baseline.

7.13.5 Slit Lamp Examination

Part I and Part II

The number and percentage of subjects within each category of slit lamp examinations outcomes will be summarized by treatment groups, visits and eyes.

The shift for 'Cornea', 'Conjunctiva', 'Iris', 'Lens' and 'Anterior Segment' will be summarized from "Normal/Clinically insignificant abnormality" or "Clinically significant abnormality" at baseline to "Normal/Clinically insignificant abnormality", or "Clinically significant abnormality" at any post-baseline visit.

The categories for the shift from baseline for 'Anterior chamber, hypopyon', 'Grading of anterior chamber cells', 'Grading of anterior chamber flare' and 'Vitreous inflammation quantification' assessments are defined as follow:

- Absent at Baseline to absent
- Absent at Baseline to present
- Present at Baseline to absent
- Present at Baseline to present

For 'Grading of anterior chamber cells' assessment, absent is defined as '0 Cells' and present is defined as any other category (except missing).

For 'Grading of anterior chamber flare' assessment, absent is defined as 'Complete absence' and present is defined as any other category (except missing).

For 'Vitreous inflammation quantification' assessment, absent is defined as '0' and present is defined as any other category (except missing).

7.13.6 Intraocular Pressure (IOP)

Part I and Part II

Intraocular pressure and change from baseline will be summarized by treatment groups, visits, and eyes.

7.13.7 Lens Opacity Grades

Part I and Part II

The number and percentage of subjects within each category of nuclear opalescence grade, nuclear color grade, cortical cataract grade and posterior cataract grade will be summarized by treatment groups, visits, and eyes.

The categories for lens opacity grades are defined as category 1, 2, 3 and 4. Category 1 includes values 1, 1.0 and 0.x. Category 2 includes values 2, 2.0 and 1.x. Category 3 includes values 3, 3.0 and 2.x. Category 4 includes values 4, 4.0 and 3.x.

CONFIDENTIAL

The shift of lens opacity grade will the summarized from "1", "2", "3", "4" at baseline to "1", "2", "3", "4" at any post-baseline visit.

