Application of AAV8-RPGR to the under-surface of the retina requires retinal detachment following vitrectomy. As such, sub-retinal injection of AAV8-RPGR carries the risks associated with vitrectomy and retinal detachment, which include intra-operative and post-operative complications: infection (most notably infectious endophthalmitis); low and elevated IOP; choroidal detachment; macular oedema; vitreous haemorrhage; visual impairment; metamorphopsia; and photopsia (Park, Marcus et al. 1995, Thompson, Sjaarda et al. 1996, Banker, Freeman et al. 1997, Cheng, Azen et al. 2001, Anderson, Fineman et al. 2006, Stein, Zacks et al. 2009, Recchia, Scott et al. 2010). Post-operative intraocular inflammation caused by vitrectomy is often associated with transient visual impairment. A long-term complication of vitrectomy is cataract formation, which may require an additional surgical procedure (cataract extraction) (Park, Marcus et al. 1995, Cheng, Azen et al. 2001, Recchia, Scott et al. 2010). To minimise inflammation resulting from potential immune responses to vector, subjects receiving AAV8-RPGR will be given a course of oral corticosteroid (see Section 8.8 for details).

Once Part I dose-escalation has been completed, and the safety and tolerability of AAV8-RPGR is demonstrated in adults, subjects ≥10 years of age will be enrolled in Part II of the study. The 10-years of age cut-off safeguards that participating pediatric subjects will be able to comply, adequately perform study assessments, and have sufficiently advanced disease that is encroaching on the macula (i.e., the AAV8-RPGR treatment administration area).

In Part II, subjects will be randomized to a high-dose $(2.5 \times 10^{11} \text{ vg})$, a low-dose $(5 \times 10^{10} \text{ vg})$, and an untreated group. This allows for comparisons in a randomized and controlled fashion, as recommended by regulators for best practices in ophthalmic gene therapy studies (FDA 2018). The sponsor, investigator and the subject will be unmasked to the study procedure and treatment (i.e. vitrectomy and sub-retinal injection). However, within the treated groups, the sponsor, investigator, and subject will be masked (i.e. double-masked) to the assigned dose. To further minimise potential bias of the treated and non-treated eye

AAV8-RPGR Version 11.0 Protocol: NSR-RPGR-01 1 Oct 2020

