9.10. Visit 9 (Month 12 ± 14 Days)

At Visit 9, the following assessments will be performed:

- Collection of safety blood samples (hematology and clinical chemistry)
- Full ophthalmic examination, including indirect ophthalmoscopy, a slit-lamp examination, IOP, anterior chamber and vitreous inflammation grading and LOCS III cataract grading
- LLVA¹
- ETDRS BCVA^{1,2}
- SD-OCT
- Fundus autofluorescence
- MAIA microperimetry¹
- Octopus 900 visual fields³
- Fundus photography
- Contrast sensitivity test¹
- •
- Immunogenicity sampling
- AE/SAE monitoring
- 1,5
- Review of concomitant medication, treatments, and procedures
 - 1. In Part II, at Month 12, LLVA, BCVA, microperimetry, contrast sensitivity, and the will be conducted by qualified masked assessors.
 - 2. Part I subjects perform BCVA assessments in triplicate at Month 12. To facilitate the additional BCVA measures, this visit should be conducted over 2 days, with BCVA measured twice on Day 1 and once on Day 2 (prior to pupil dilation). All 3 BCVA values must be recorded in the eCRF.

3. Octopus 900 perimeter is specified for visual field assessments only in Part II.

Subjects who develop cataracts should undergo cataract surgery if deemed clinically necessary; if surgery is performed, it should be carried out at least 4 weeks before Visit 9 (Month 12) or Visit 11 (Month 24) for Part II and Part I subjects, respectively.

Although the visit will still be considered out-of-window, if Part II subjects are unable to attend their final 12-month visit during the protocol-defined window, they should return to the site to complete this visit as soon as it is possible for them to do so. This will be considered their 12-month visit. Delays will be identified as PDs on a case-by-case basis by the Sponsor based on information provided by the site; this will include but is not limited to scenarios such as site closure, travel bans, medical travel prohibitions, patient illness, etc.

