12.7.2. Ocular Safety Evaluations

IOP and changes from baseline in IOP, abnormal slit lamp examination findings and indirect ophthalmoscopy findings, and anterior chamber and vitreous inflammation grading will be summarised by visit and eye.

Lens opacity categories and shifts from baseline will be summarised by visit and eye.

Categories of fundus photography findings (none/mild/moderate/severe) will be summarised by visit and eye.

The number of subjects with a 5, 10 and 15letter decrease from baseline in BCVA will be tabulated by visit and by eye.

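### The lens-opacity tables have no category for a lens removed during the study, so operated eyes are expected to drop out of the final-visit figures

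*SAP*

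**What the plan says.** SAP 7.13.7 summarises nuclear opalescence, nuclear colour, cortical and posterior cataract grades separately, by treatment group, visit and eye. "The categories for lens opacity grades are defined as category 1, 2, 3 and 4". At the lower end, "Category 1 includes values 1, 1.0 and 0.x". The shift table runs from the same four categories "at baseline to '1', '2', '3', '4' at any post-baseline visit". Protocol 12.7.2 asks for the same output: "Lens opacity categories and shifts from baseline will be summarised by visit and eye". Neither section gives a category or rule for an eye whose lens is removed during follow-up.

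On missing data, SAP 7.13 states "All safety analyses will be summarized based on observed case", and SAP 7.6 rules out imputation for safety.

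On cataract as a risk, Protocol 6.3 says "A long-term complication of vitrectomy is cataract formation, which may require an additional surgical procedure". Section 8.8 lists cataract among the side effects to watch for during oral steroids.

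On surgery, Protocol 9.10 says "Subjects who develop cataracts should undergo cataract surgery if deemed clinically necessary" and, on timing, "it should be carried out at least 4 weeks before Visit 9 (Month 12) or Visit 11 (Month 24" (Part II and Part I respectively). Protocol 6.1, Protocol 11.4 and SAP 6.3 use 'may' where 9.10 uses 'should'. All four make surgery conditional on clinical need, and all four apply the timing only if surgery is done.

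**The concern.** A grade of lens opacity needs a natural lens. The plan expects some lenses to be removed, times the removal before the last safety visit, and reports that visit on observed cases in categories that only a natural lens can fill. The missing grade is then caused by the outcome being measured, because the eye has no grade once its cataract has progressed far enough to need an operation.

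The loss should be uneven. Only dosed study eyes undergo vitrectomy. In Part II the oral steroid course goes to the treated groups (Table 3, footnote l). Clinically significant cataract is an example of an excluded condition at entry (Section 7.3), so an extraction on study mostly reflects progression after enrolment. The by-visit comparison of dosed eyes with untreated controls (Part II) and with fellow eyes (both parts) would therefore lean toward showing less lens harm than occurred. What is at stake is whether the graded lens output for a named procedural risk can be interpreted. No hypothesis test is affected.

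**Working it through.** The plan gives no figure to reproduce, so the check is a reading of the text followed by a counting illustration.

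**Reading**

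1. Lens grading is part of the full ophthalmic examination, done at every visit including the last (Protocol Table 3).
2. If surgery is done under the stated timing, it comes before Month 12 (Part II) or Month 24 (Part I).
3. At that visit the eye has no natural lens. The eCRF coding of this is not shown. If the grade is left missing, the eye leaves both numerator and denominator on observed cases. If 0 is entered, the eye could be counted in category 1.
4. The shift table refers to any post-baseline visit, so a pre-operative grade may survive there. The SAP does not say whether the worst grade is taken. That grade could be up to about 3 months old between Months 3 and 12, and up to about 6 months old between Months 12 and 24 in Part I. Unscheduled visits also include lens grading (Protocol 9.14), but SAP 7.3 analyses by nominal visit.

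**Counting illustration**

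Inputs: n = 10 eyes in a dosed arm (the treated-group size in SAP 6.6). k = eyes extracted before the final visit (assumed). m = eyes with a natural lens in category 3-4 on one grade scale (assumed). All eyes attend, and extracted eyes are recorded as missing.

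- Table as planned: m / (n − k)
- Category 3-4 or extracted, full denominator: (m + k) / n
- Table if an absent lens is coded 0: m / n

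| k | m | As planned | Category 3-4 or extracted | Coded 0 |
|---|---|---|---|---|
| 1 | 0 | 0/9 = 0% | 1/10 = 10% | 0/10 = 0% |
| 2 | 0 | 0/8 = 0% | 2/10 = 20% | 0/10 = 0% |
| 3 | 0 | 0/7 = 0% | 3/10 = 30% | 0/10 = 0% |
| 4 | 0 | 0/6 = 0% | 4/10 = 40% | 0/10 = 0% |
| 1 | 1 | 1/9 = 11.1% | 2/10 = 20% | 1/10 = 10% |
| 3 | 1 | 1/7 = 14.3% | 4/10 = 40% | 1/10 = 10% |

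The two main columns are not the same quantity: one is a grade prevalence, the other a composite of grade or extraction. They describe the same thing on a given scale only if every extracted eye was in category 3-4 on that scale before surgery. If j of the k extracted eyes were, the share with their pre-operative grades kept is (j + m)/n, and the planned figure is lower than this when j/k > m/(n − k). For k = 3 and m = 1 the threshold is 1/7, so j = 1 is enough: (1 + 1)/10 = 20% against 14.3%. With j = 0 the planned figure is slightly higher, 14.3% against 1/10 = 10%. The understatement therefore falls on the scale or scales that the operated cataracts had raised.

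**The case against.** The strongest reply has four parts.

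*The signal is captured elsewhere.* Adverse events include worsening of pre-existing conditions (Protocol 11.2.1.1). They are tabulated by preferred term, eye, group, severity and relation to the procedure (SAP 7.13.1), and the slit-lamp examination has its own 'Lens' shift (SAP 7.13.5). This stands, and it limits the point. A reader might infer that cataract is hidden from the safety output as a whole; it is not. But those tables do not repair the graded ones. The slit-lamp shift has two levels and neither identifies an extracted lens. SAP 7.10 tabulates medications only, and I found no planned table of extractions by arm and eye.

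*Surgery is not required.* A reader might take Section 9.10 to mean that the protocol directs extraction before the last visit. The documents do not support that: three of the four statements say 'may', and all are conditional. The passages must be reconciled. The point does not depend on the outcome, since a grade is lost whenever surgery is done.

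*The mechanism is partly assumed.* The eCRF coding of an absent lens and the percentage denominator are not stated. This also stands. Missing is the natural consequence of having no lens to grade, and a code of 0 would hide the cataract in a different way.

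*The effect may be small.* Part II follow-up is 12 months, entry excludes clinically significant cataract, and safety has no formal testing (Protocol 12.7). All true. A reader might still infer that the graded tables would point the opposite way from the adverse event tables. Nothing supports that: there are no comparator figures, so attenuation in dosed eyes is the most that can be claimed.

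**Conclusion.** The point holds for the graded lens tables and no further. As written, the by-visit tables at Month 12 (Part II) and Month 24 (Part I) are expected to lose operated eyes for a reason tied to the outcome, and so to understate lens worsening mainly in dosed study eyes. For the shift table the loss is possible but not certain.

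The size is unknown because no extraction rate is given. In arms of about 10, each extraction adds 1/10 = 10 percentage points to a category-3-4-or-extracted share on the full denominator, and the planned table would show none of it.

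The conclusion rests on three assumptions: some extractions occur and follow the stated timing; an absent lens is recorded as missing or 0; and the operated eyes were high on at least one of the four scales. The last is inferred from surgery being clinically necessary, since no grade threshold is stated. Efficacy and formal inference are untouched. It is a modest defect, but cheap to remove.

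**What to change.** In SAP 7.13.7, add 'lens extracted since baseline' as a separate category, ranked worst, in the by-visit and shift tables for all four grades. Carry it to every later visit attended and keep those eyes in the denominator. Let it override any grade entered for an absent lens, so that a 0 cannot be read as category 1. Show eyes already without a natural lens at baseline separately. Derive the extraction date from the procedures that Protocol 8.8 already has recorded at every visit. Separately, reconcile the cataract-surgery wording in Protocol 6.1, 9.10 and 11.4 and SAP 6.3.

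The cost is SAP wording and one derived variable, with no new assessment and no change to the efficacy analysis. The downside is that the cataract figures for the dosed arms will look less favourable.
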